Patients will be examined at their review appointment by a member of the research team or treating clinician according to the following Budapest Criteria:

- A: continuing pain, which is disproportional to any inciting event
- B: The patient must report at least one symptom in three of the four following categories:
  - Sensory- reports of hyperaesthesia and/or allodynia
  - Vasomotor – reports of temperature asymmetry and/or skin colour changes and/or skin colour asymmetry
  - Sudomotor/oedema – reports of oedema and/or sweating changes and/or sweating asymmetry
  - Motor/trophic – reports of decreased range of motion and/or motor dysfunction (weakness/tremor/dystonia) and/or trophic changes (hair/nail/skin)
- C: The clinician must observe at least one sig at the time of the evaluation in two or more of the following categories:
  - Sensory- evidence of hyperalgesia (to pinprick) and/or allodynia and/or deep somatic pressure and/or joint movement
  - Vasomotor – evidence of temperature asymmetry and/or skin colour changes and/or skin colour asymmetry
  - Sudomotor/oedema – evidence of oedema and/or sweating changes and/or sweating asymmetry

- 
- Motor/trophic – evidence of decreased range of motion and/or motor dysfunction (weakness/tremor/dystonia) and/or trophic changes (hair/nail/skin)
  - D: There is no other diagnosis that better explains the signs and symptoms

If a patient is unable to attend their appointment in person, a Telehealth appointment and videoconference examination will be utilised instead of a face-to-face appointment.

This information will be recorded in RedCap database managed by Monash University. Patients who meet the above criteria will be diagnosed with complex regional pain syndrome and referred to physiotherapy for management of this condition. They will be told to continue their treatment medication. Patients will then be removed from the trial follow-up (as you cannot have CRPS twice from the same event).

Patients diagnosed with CRPS will be communicated to the lead researcher via email and subsequently entered into the trial database as meeting the outcome.

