### **7.5.4 Telehealth consultations**

In light of the recent coronavirus pandemic and shift to telehealth consultations, the need for potential telehealth follow up has been made. It is expected that patients will be followed up by standard face-to-face appointments but, if required, follow up can be via videoconference using secure videoconference programs as recommended by the Department of Health – these are Health Direct (Peninsula Health) or CoviU (Frankston Private Hospital, Holmesglen Private Hospital, Cabrini Brighton Private Hospital and Beleura Private Hospital). These videoconferencing systems are secure and recommended by the federal Department of Health for telehealth consultations.

---

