#### **9.2.2 Data Capture Methods and Storage**

Study investigators will be briefed on how to record information in their assessment and consultation notes for the trial as per the protocol using RedCap. Education material and training on the use of RedCap will be provided by the Principal Investigator.

Clinicians will document the following assessment criteria in RedCap at each two week, six week, twelve week and twenty-six week follow up point:

---

A: Does the patient report a history of:

- sensory changes (hyperaesthesia and/or allodynia)
- vasomotor changes (temperature asymmetry, skin colour changes and/or skin colour asymmetry)
- sudomotor/oedema changes (oedema, sweating change or sweating asymmetry)
- motor/trophic changes (decreased range of motion and/or motor dysfunction and/or weakness/tremor/dystonia and/or trophic changes of hair/nails/skin?)

---

B: Does the clinician observe:

- sensory changes (hyperaesthesia and/or allodynia)
- vasomotor changes (temperature asymmetry, skin colour changes and/or skin colour asymmetry)
- sudomotor/oedema changes (oedema, sweating change or sweating asymmetry)
- motor/trophic changes (decreased range of motion and/or motor dysfunction and/or weakness/tremor/dystonia and/or trophic changes of hair/nails/skin?)

---

C: Is there another diagnosis that better explains the signs and symptoms during today's history and examination?

Yes  
 No

---

D: Is the patient's pain disproportionate to the inciting event?

Yes  
 No

---

If the patient responds yes to three out of four questions in part A, AND the clinician observes two out of four signs in part B, AND answers yes to C and D, the patient meets the criteria for CRPS diagnosis.

Yes  
 No

Does the patient meet the criteria for CRPS diagnosis?

---

How has the patient felt since their last visit? (eg. fine, unwell, nauseated, in pain)

\_\_\_\_\_

---

Has the patient had any side effects to the medication such as abdominal upset, back pain, nausea or vomiting?

Yes  
 No

---

Has the patient taken the medication as prescribed?

Yes  
 No

The diagnosis of CRPS will be made if the patient meets the Budapest criteria, and patients will be referred to physiotherapy for pain management. The investigator will record whether the patients was diagnosed with CRPS in the EMR and communicate this back to the patient's General Practitioner via a clinical letter (this is standard practice in the event of a post-operative complication).

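### A video visit can replace the in-person CRPS examination, but the form items shown cannot distinguish a sign that was not tested from one that was absent

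*Protocol*

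**What the plan says.** Protocol section 7.4 (Description of procedures) provides that, for a patient who cannot attend in person, "a Telehealth appointment and videoconference examination will be utilised instead of a face-to-face appointment". Section 7.5.4 (Telehealth consultations) sets the expected use: "It is expected that patients will be followed up by standard face-to-face appointments but, if required, follow up can be via videoconference". Neither section restricts which visits may be by video, adapts the criteria, or says how to handle an examination that could be done only in part.

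The sign criterion in section 7.4 reads "The clinician must observe at least one sig at the time of the evaluation in two or more of the following categories". The categories are:

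- sensory: "evidence of hyperalgesia (to pinprick) and/or allodynia and/or deep somatic pressure and/or joint movement"
- vasomotor: a temperature difference, or altered or unequal skin colour
- sudomotor/oedema: swelling, or altered or unequal sweating
- motor/trophic: reduced movement, motor dysfunction, or hair, nail or skin change

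The form items reproduced in sections 7.4 and 9.2.2 introduce the signs with "B: Does the clinician observe". They give one tick box per category and ask for two of four. Among the items shown there is no option for a category that could not be assessed and no item for visit mode.

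Section 3.2 counts a participant as a case if the criteria are met at any of the four reviews. It also lists successful follow-up at the set time points as a feasibility outcome. Section 11.3 reports six-month incidence as a proportion of the study sample, compares arms by Cox regression, and plans a sensitivity analysis on individual criteria.

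**The concern.** The outcome depends partly on signs that a clinician elicits by touch or instrument. If those cannot be tested at a video visit and the form stores the result as an unticked box, a partial examination with fewer than two visible signs is indistinguishable from a complete negative one.

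Three results could suffer:

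- **Incidence.** A true case missed this way stays in the denominator as a non-case.
- **Feasibility.** A visit that could not deliver the full outcome examination can be counted as successful follow-up, although the data collection procedure is part of the primary objective.
- **The analysis by individual criteria.** Sensory signs that were never tested would enter as absent.

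The planned handling of dropout (censoring, multiple imputation, covariates for dropout) does not reach this problem, because such a visit is neither missed nor lost.

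**Working it through.** The protocol gives no event rate, video share or diagnostic sensitivity, so there is no stated figure to reproduce. The numbers below illustrate size on stated assumptions.

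**Step 1. What video can show, category by category**

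| Category | Hard to test by video | Still visible |
|---|---|---|
| Sensory | pinprick, deep pressure, clinician-elicited allodynia | possibly pain on movement by the patient |
| Vasomotor | temperature | skin colour |
| Sudomotor/oedema | sweating, in part | oedema |
| Motor/trophic | strength, in part | range of motion, tremor, hair, nails, skin |

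Three of four categories keep a visible sign, so the two-category rule can still be met. The sensory category is the one mainly lost.

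**Step 2. Direction.** An untested sign leaves the box blank. A blank can only reduce the count towards two, so this mechanism can turn a true case into a non-case but not the reverse.

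**Step 3. Size at one video visit.** Assume that a true case shows each category independently with probability p. With four testable categories, P(at least two) = 1 − (1−p)^4 − 4p(1−p)^3. With three, it is 3p²(1−p) + p³. The difference is 3p²(1−p)².

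| p (assumed) | Four testable | Three testable | Loss | Ratio r |
|---|---|---|---|---|
| 0.6 | 0.821 | 0.648 | 0.173 | 0.79 |
| 0.7 | 0.916 | 0.784 | 0.132 | 0.86 |
| 0.8 | 0.973 | 0.896 | 0.077 | 0.92 |

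The loss is about 8 to 17 points. If a further 20% of signs in the other three categories are also missed on video, p becomes 0.8p for those three, and r falls to 0.57, 0.64 and 0.72.

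**Step 4. Size across the trial.** If a share s of cases have a video visit as their only informative visit, the proportion detected relative to all in-person assessment is 1 − s(1−r).

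| s (assumed) | r = 0.92 | r = 0.79 | r = 0.65 |
|---|---|---|---|
| 5% | 99.6% | 99.0% | 98.3% |
| 20% | 98.4% | 95.8% | 93.0% |
| 50% | 96.0% | 89.5% | 82.5% |

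A case with another informative visit has a further chance of detection, which shrinks these losses. Section 7.4 ends trial follow-up only after a diagnosis, so a missed case remains under review. No scheduled visit follows week 26, so a case missed by video there is not recovered.

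**Step 5. Arm comparison.** If detection is equally reduced in both blinded arms and false positives are unaffected, the ratio is preserved. With assumed true risks of 20% and 10% and 80% detection, the observed risks are 16% and 8%. The ratio stays at 0.5, while the difference shrinks from 10 to 8 points.

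**The case against.** The strongest reply is that this is a contingency. Video is for patients who cannot attend, the expected mode is face-to-face, two visible categories are enough, and four reviews give repeated chances. The independence assumption may also overstate the loss: if signs cluster in true cases, losing one category matters less. A patient might touch or move the limb on camera, and the form describes sensory signs more loosely than the criteria do. All of this stands, and it limits the size.

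A reader might infer three stronger conclusions that the protocol does not support.

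- **That CRPS will be under-diagnosed in this trial.** No video share is given, so only the direction at a video visit is established.
- **That the treatment comparison is biased.** Patients and clinicians are blinded, and with equal loss in both arms the ratio holds. Bias would need video use or sign visibility to differ by arm.
- **That visit mode is certainly not captured and can never be recovered.** Sections 7.4 and 9.2.2 do not show the whole case report form: adverse-event details and the discontinuation page, required elsewhere, are not among those items. Section 9.2.1 also calls for a note in the electronic medical record, so visit mode may be traceable. Likewise, that a blank means absent is read from the layout and counting rule; the protocol does not say so in words.

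It can also be said that a face-to-face-only analysis belongs in an analysis plan. That is fair for the analysis, but not for the data: which signs were tested cannot be reconstructed later if it was never recorded.

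**Conclusion.** The point holds as a data-capture weakness with a known direction and an unknown, probably small, overall size. Video is a full substitute under an unchanged sign rule, and the form items shown do not separate untested from absent.

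The loss of about 8 to 17 points applies to a single video visit. It rests on independent categories, assumed probabilities of 0.6 to 0.8, and loss of the sensory category alone. It is not an estimate for the trial.

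The practical consequences are a somewhat low incidence estimate, most of all where the week 26 visit is by video, and a follow-up count that can include incomplete outcome examinations. The rate ratio should be little affected. The second consequence deserves attention because this is a feasibility study: whether video can deliver the outcome is something the later trial needs to know.

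**What to change.** Keep telehealth, and make these changes:

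1. Add a visit-mode item (in person or video) to the visit form.
2. Add a not-assessable option for each of the four sign categories.
3. For the feasibility and incidence reports, count a video visit that does not meet the criteria and has at least one non-assessable category as an incomplete outcome assessment, not as a negative one.
4. Report the number of such visits.
5. Repeat the incidence and Cox analyses on face-to-face assessments only, as a sensitivity analysis.

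The counting rule in item 3 is aimed at feasibility and incidence because it changes little in the main Cox model: a negative and an incomplete visit both leave the participant at risk until the next review, unless it was the last one. Item 5 covers the Cox analysis.

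The cost is one form item, one extra option in four places, and one sensitivity analysis. The downside is that a few more visits will be counted as incomplete.

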#### **5.2.6 Measurement of participant adherence**

Patients will be asked at their two-week, six-week, twelve-week and twenty-six week reviews whether they had been adherent with taking their medication. Adherence will be recorded in the medical record. If patients miss more than three doses at any stage in the preceding two weeks, they will be deemed non-adherent to the treatment protocol and participation withdrawn. Data up to that point will be analysed in the groups to which they were randomised following the intention-to-treat principle, but adherence will be noted and documented.

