All hospital registrars and orthopaedic consultants will be given a verbal presentation to introduce the research project and the study investigators involved in the trial. This will be done at an orthopaedic weekly business meeting for approximately one hour. Education on trial design and CRPS examination and history will be provided. Study researchers will conduct follow-up history and examination.

Assessment at two weeks, six weeks, twelve weeks and twenty-six weeks is standard treatment for most bony and soft tissue injuries of the lower limb and does not deviate from normal procedure.

If a patient is diagnosed with CRPS, they will be referred to physiotherapy as per usual care. The method for which they are referred will depend on whether the patient is referred in the public or private systems:

- Public: a written referral will be made to the Physiotherapy Department at Peninsula Health. This is standard practice for a patient diagnosed with CRPS in this institution.
- Private: a written referral will be made to the patient's regular physiotherapist. If the patient does not have a regular physiotherapist, a choice of local, experienced physiotherapists will be offered for a referral and a written referral will be made. This is standard practice for management of CRPS in this system.

Patients will also be asked at each review appointment if they have adhered with the medication and if they are experiencing any side effects.

---

How has the patient felt since their last visit? (eg. fine, unwell, nauseated, in pain)

\_\_\_\_\_

---

Has the patient had any side effects to the medication such as abdominal upset, back pain, nausea or vomiting?

Yes  
 No

---

Has the patient taken the medication as prescribed?

Yes  
 No

If patients have skipped up to three consecutive dose of their medication, they will be

---

deemed 'non adherent and a note will be made on their Electronic Medical Record but will still be analysed to where they were randomised. If patients skip one dose they will be advised to simply continue the medication and not 'make up' a dose.

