## **6.3 Capturing and eliciting adverse event/reaction information**

Adverse events and adverse reactions (non-serious and serious) will be captured from the time of administration of the medication until 30 days following the final dose (fifty days after commencement of the trial) and will be followed until resolution or stabilisation.

At every trial visit participants will be asked "How have you felt since your last visit?" in order to elicit any medically related changes in their well-being. They will also be asked if they have been hospitalised, had any accidents, used any new medication or changed concomitant medication regimens. In addition, AEs will be documented from physical examination

---

findings, clinically significant lab results or other documents (including participant diaries and correspondence from their primary care physician) that are relevant to participant safety. This will be recorded in the patient's medical record as well as communicated with members of the research team.

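### Patients diagnosed with CRPS are told to keep taking the capsules but are removed from trial follow-up, so scheduled adverse-event and adherence questions can end early

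*Protocol*

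**What the plan says.** Section 7.4 (Description of procedures) gives two consecutive instructions for a patient who meets the Budapest criteria at a review. The first is "They will be told to continue their treatment medication". The second is "Patients will then be removed from the trial follow-up (as you cannot have CRPS twice from the same event".

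Other parts of the protocol place drug-related questioning in those same reviews:

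- Section 6.3 (Capturing and eliciting adverse event/reaction information) requires capture "from the time of administration of the medication until 30 days following the final dose". The means is a question put at every trial visit: "How have you felt since your last visit".
- Section 5.2.6 (Measurement of participant adherence): "Patients will be asked at their two-week, six-week, twelve-week and twenty-six week reviews whether they had been adherent".
- Section 7.4 itself: "Patients will also be asked at each review appointment if they have adhered with the medication and if they are experiencing any side effects".
- Section 9.2.2 (Data Capture Methods and Storage) shows the CRPS criteria, the side-effect question and the adherence question together as one assessment, completed at each of the four follow-up points.

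No section keeps safety or adherence reviews going for a diagnosed patient who stays on the capsules.

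**The concern.** The stated reason is that a patient cannot have CRPS twice from one event. That is a reason to stop counting the outcome. It says nothing about a product the patient has just been told to keep taking. Read as written, the instruction cuts short the adverse-event window in section 6.3 and the adherence schedule in section 5.2.6.

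It also produces an odd ordering. Under section 5.2.9, and again under the later section on treatment discontinuation, patients who stop the capsules stay in scheduled follow-up. Even after withdrawal of consent the protocol asks for reasonable efforts at safety evaluation. A diagnosed patient still on the capsules would get less scheduled safety follow-up than either group.

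Two things are at stake. Patient-reported compliance and complications are listed in section 3.2 among the outcomes for the primary feasibility objective, so the loss touches what the trial is for. The loss is also defined by the efficacy outcome: if vitamin C changes the incidence of CRPS, safety and adherence data would be cut short more often in one arm than in the other. Section 11.2.1 allows no substitution for missing adverse-event or adherence data.

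**Working it through.** The protocol gives no figure of its own to reproduce. The check is day arithmetic on its schedule, with day 0 as surgery.

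**Inputs**

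- First capsule within 72 hours of surgery (section 4.4.2): day 0 to day 3.
- Fifty daily capsules (synopsis).
- Adverse-event capture to 30 days after the last dose (section 6.3).
- First review: day 7–14 (synopsis) or day 10–14 (section 3.2).
- Second review: five to six weeks, day 35–42 (both).
- Third review: eleven to fourteen weeks, day 77–98 (synopsis), or ten to twelve weeks, day 70–84 (section 3.2).
- Last review: 26 weeks, day 182.

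**Fixed points**

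- Last dose = start + 49: 0 + 49 = day 49 to 3 + 49 = day 52.
- Window closes = last dose + 30: 49 + 30 = day 79 to 52 + 30 = day 82.

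**What remains when follow-up ends at the diagnosing review**

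| Diagnosis at | Capsules left | Window days left |
|---|---|---|
| First review, day 7–14 | 49 − 14 = 35 to 52 − 7 = 45 | 79 − 14 = 65 to 82 − 7 = 75 |
| First review, day 10–14 | 35 to 52 − 10 = 42 | 65 to 82 − 10 = 72 |
| Second review, day 35–42 | 49 − 42 = 7 to 52 − 35 = 17 | 79 − 42 = 37 to 82 − 35 = 47 |
| Third review, day 77–98 | 0 | at most 82 − 77 = 5 |
| Third review, day 70–84 | 0 | at most 82 − 70 = 12 |
| 26 weeks, day 182 | 0 | 0 |

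As a share of the 50-capsule course, a first-review diagnosis leaves 35/50 = 70% to 45/50 = 90% without scheduled questions. A second-review diagnosis leaves 7/50 = 14% to 17/50 = 34%.

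**Which questions are lost**

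- *First-review diagnosis.* The second review, the only other one during dosing, is lost, and so is the third.
- *Second-review diagnosis.* No later review falls during dosing. The third comes 70 − 52 = 18 to 98 − 49 = 49 days after the last dose, anywhere from 82 − 70 = 12 days before the window closes to 98 − 79 = 19 days after. The practical loss is the look-back questioning at that review.
- *Third-review diagnosis.* The next review is 182 − 82 = 100 to 182 − 79 = 103 days after the window closes, so no scheduled questioning inside the window is lost. At most, look-back over the last 5 days (synopsis timing) or 12 days (section 3.2 timing) is lost.

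**The adherence rule.** Section 5.2.6 judges non-adherence over a short look-back: "If patients miss more than three doses at any stage in the preceding two weeks". At the second review that look-back starts on day 35 − 14 = 21 to 42 − 14 = 28 and lies wholly within dosing. At the third it starts no earlier than day 70 − 14 = 56, after the last dose. This rule therefore loses dosing data only after a first-review diagnosis. At the third review only the since-last-visit question and the taken-as-prescribed question can recover the end of dosing.

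**An ambiguity in section 6.3.** A bracket there mentions fifty days from the start of the trial. If it meant that the window itself closes at about day 50, a diagnosis at either of the first two reviews would still cut it short.

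**How many patients.** The protocol does not say. Purely as an assumed range, take CRPS incidence of 5–30% and 25–75% of diagnoses at the first two reviews. Then between 100 × 0.05 × 0.25 = 1.25 and 100 × 0.30 × 0.75 = 22.5 of about 100 participants would be affected. This pools the two reviews, so it does not size the more serious first-review case.

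**The case against.** The strongest reply is that only outcome follow-up was meant to end. The sentence closes a passage about the Budapest examination, and its bracketed reason fits outcome ascertainment alone. The safety section makes no exception for diagnosed patients, so the narrow reading makes the protocol consistent. This may well be the intention. It is not what the text says, however: the removal is from trial follow-up without limit, the adherence and side-effect questions sit in the same reviews and on the same form, and the assessing staff include rotating junior doctors who will act on the wording.

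The second reply is that other routes remain. Section 5.2.5 asks for leftover capsules back, records reasons for departing from the regimen and reconciles supplies at the end of the trial, none of which depends on a review. Medication-related events are followed to resolution (7.5.2), patients are asked to report unscheduled visits (7.5.3), and diaries and primary-care letters feed adverse-event recording (6.3). Many patients would also still be seen clinically. This stands, and it limits the harm, especially for adherence. None of these routes is a scheduled question about tolerability.

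Third, the day counts can look larger than the loss. After a second-review diagnosis the 37–47 window days correspond to one retrospective set of questions at the third review, and that review may fall after the window has closed. This is correct. The serious case needs a diagnosis at day 7–14, whose frequency is unknown, and section 2.2 notes that diagnosis is often delayed.

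Finally, the product is low-risk, adverse events are only to be tabulated, and stopping outcome follow-up at the first event is ordinary practice for a time-to-event endpoint. All true; these points bear on severity and leave the contradiction in place.

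**Conclusion.** The concern holds. As written, the protocol keeps diagnosed patients on the capsules and ends the reviews at which it promises to ask them about adverse events and adherence. The loss is material after a first-review diagnosis, modest after a second-review diagnosis, and negligible for on-drug data after that.

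The consequences are limited. The Cox analysis of time to first CRPS does not need follow-up beyond the event. The lost-to-follow-up rate is also unaffected, because the protocol's definition requires two missed visits and failed contact.

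The conclusion assumes that sites follow the sentence literally and that the timing windows are kept. The number of patients affected cannot be fixed from the protocol. The point should be corrected, but it does not threaten the trial.

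**What to change.** In section 7.4, replace the sentence removing diagnosed patients from follow-up with a rule along these lines: the CRPS event time is fixed at the first positive visit and no further CRPS outcome is counted; the participant continues the scheduled reviews for adverse events and adherence until at least 30 days after the final dose, up to and including the first review held once that period has ended.

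The last clause matters because a third review held before day 79–82 would otherwise leave up to 12 window days unasked about. If only outcome follow-up was ever meant to end, this wording simply says so.

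The cost is one sentence and a little extra data entry. The visits themselves are largely in place: section 7.4 says that assessment at two weeks, six weeks, "twelve weeks and twenty-six weeks is standard treatment for most bony and soft tissue injuries of the lower limb".
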